4.4 Secondary Safety Outcomes

Both Arms:

- 1. Incidence of SICH, by ECASS III definition, within 24 (-6/+24) hours post randomization (time zero)
- Incidence of neurological deterioration from baseline NIHSS score through Day 5-7/discharge (whichever is earlier) post randomization (time zero). Neurological deterioration is defined as ≥ 4 point increase in the NIHSS score from the baseline score.

Document Number: CDM10000146

Treatment Arm only:

- 3. Incidence of procedure-related and device-related serious adverse events (PRSAEs and DRSAEs) through 24 (-6/+24) hours post randomization (time zero), as adjudicated by the clinical events committee (CEC), and defined as:
 - vascular perforation
 - intramural arterial dissection
 - embolization to new territory
 - access site complication requiring surgical repair or blood transfusion
 - intra-procedural mortality
 - device failure (*in vivo* breakage)
 - any other complications adjudicated by the CEC to be related to the procedure

5 Study Design

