13.2.1 Clinical Events Committee (CEC)

The CEC will include specialists in stroke neurology and/or neuro-intervention as well as other experts with the necessary therapeutic and subject matter expertise who are not participating in the trial and have no affiliation with Stryker NV. CEC responsibilities, qualifications, membership, and committee procedures are outlined in the CEC charter. The CEC will be responsible to review and adjudicate the following protocol-defined safety outcome measures and relevant adverse events reported by study investigators. Relevant information and source documents will be provided to assist with their review and adjudication of events.

- Vessel perforation
- Intramural Arterial dissection
- Symptomatic ICH
- Embolization to a new territory
- Neurological worsening (associated with a 4 or more point increase in NIHSS) or possible or confirmed evolution/progression of the index stroke
- All deaths

Document Number: CDM10000146

In cases where their expertise is required the CEC will be asked for an opinion on the following events. However, the Stryker NV safety department will be responsible for their initial review and coding and they will not automatically be sent to the CEC for adjudication:

- *In vivo* device failure (*in vivo* breakage)
- Access site complication requiring surgical repair or blood transfusion
- Other confirmed or suspected Procedure and/or Device-related SAEs with an outcome other than death occurring at any time during subject participation

13.2.2Data Monitoring Committee (DMC)

The DMC will include specialists in stroke neurology and/or neuro-intervention as well as biostatistics, who are not participating in the trial and have no affiliation with Stryker NV. The DMC is responsible for monitoring subject safety through pre-defined, periodic review of the clinical study safety data. DMC responsibilities, qualifications, membership, meeting frequencies, and procedures are outlined in the DMC charter.

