**Pre-stroke disability:** Obtained at baseline, but representative of the subject's status before the index stroke, assessed by mRS on medical history obtained from subject's medical chart, or family members.

Procedure-Related Serious Adverse Event (PRSAE): Procedure-related events that include, but are not limited to vascular perforation or intramural arterial dissection,

Document Number: CDM10000146

symptomatic ICH, embolization to a new territory, or access site complication requiring surgical repair or blood transfusion, intra-procedural death, or device failure (*in vivo* breakage).

**Protocol Deviation:** Any alteration/modification to the current IRB/EC-approved protocol. The protocol includes the detailed protocol, protocol summary, consent form, recruitment materials, questionnaires, and any other information relating to the research study. Note: Any permanent change to the protocol constitutes an amendment that must be submitted to the Institutional Review Board/Ethics Committee for approval prior to initiation. Deviations may be further classified as:

- Major deviation: a deviation that may impact subject safety, affect the integrity of study data and/or affect subject's willingness to participate in the study, such as but not limited to: enrollment without obtaining appropriate informed consent; violation of inclusion/exclusion criteria; randomization irregularities including treatment arm crossover; confounding procedure by using non allowed therapies; non reporting of SAEs/UADEs and study product non conformities; and protocol required assessments repeatedly not completed at the required time windows
- Minor deviation: a deviation that does not impact subject safety, compromise the integrity of study data and/or affect subject's willingness to participate in the study, such as but not limited to: follow up assessments not conducted or conducted outside of the required time windows.

Protocol Exception: Any single protocol deviation that is approved by Stryker NV prior to its initiation, and documented in writing. Note: Any permanent change to the protocol constitutes an amendment that must be submitted to the IRB/EC for approval prior to initiation.

Remote Intracerebral Hemorrhage (RIH): Any intraparenchymal hemorrhage remote from the ischemic field.

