3.1.4. Secondary Safety Outcome

Both Arms:

- a. Incidence of SICH, by ECASS III definition, within 24 (-6/+24) hours post randomization (time zero)
- b. Incidence of neurological deterioration from baseline NIHSS score through Day 5-7/discharge (whichever is earlier) post randomization (time zero). Neurological deterioration is defined as ≥ 4 point increase in the NIHSS score from the baseline score.

Treatment Arm:

- c. Incidence of procedure-related and device-related serious adverse events (PRSAEs and DRSAEs) through 24 (-6/+24) hours post randomization (time zero) as adjudicated by the clinical events committee, and defined as:
 - a. vascular perforation
 - b. intramural arterial dissection
 - c. embolization to a new territory
 - d. access site complication requiring surgical repair or blood transfusion
 - e. intra-procedural mortality
 - f. device failure (*in vivo* breakage)
 - g. any other complications adjudicated by the CEC to be related to the procedure

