5.4. Analysis of Secondary Safety Outcome

Both Arms:

- a. Incidence of SICH, by ECASS III definition, within 24 (-6/+24) hours post randomization (time zero) will be presented by providing the count and percentage for each treatment arm. The difference in the percentage between two arms and the 95% CI for the difference will be calculated using the normal approximation to binomial. P-values will be calculated by the Chi-squared test or Fisher's exact test as appropriate. Relative Risk (RR) was provided as Trevo thrombectomy plus medical management / medical management.
- b. Incidence of neurological deterioration from baseline NIHSS score through Day 5-7/discharge (whichever is earlier) post randomization (time zero). Neurological deterioration is defined as ≥ 4 point increase in the NIHSS score from the baseline

STRYKER CONFIDENTIAL - THIS DOCUMENT CONTAINS CONFIDENTIAL AND PROPRIETARY INFORMATION THAT IS THE PROPERTY OF STRYKER CORPORATION. NEITHER THIS DOCUMENT NOR THE INFORMATION HEREIN MAY BE REPRODUCED, USED, OR DISCLOSED TO ANY THIRD PARTY WITHOUT THE PRIOR WRITTEN CONSENT OF STRYKER CORPORATION

score, which will be presented by providing the count and percentage for each treatment arm. The difference in the percentage between two arms and the 95% CI for the difference will be calculated using the normal approximation to binomial. P-values will be calculated by the Chi-squared test or Fisher's exact test as appropriate. Relative Risk (RR) was provided as Trevo thrombectomy plus medical management / medical management.

Treatment Arm:

Incidence of procedure-related and device-related serious adverse events (PRSAEs and DRSAEs) through 24 (-6/+24) hours post randomization (time zero) as adjudicated by the clinical events committee, and defined as:

- a. vascular perforation
- b. intramural arterial dissection
- c. embolization to a new territory
- d. access site complication requiring surgical repair or blood transfusion
- e. intra-procedural mortality
- f. device failure (*in vivo* breakage)
- g. any other complications adjudicated by the CEC to be related to the procedure

The number of Subjects with SAEs will be summarized by CEC adjudicated category described as above, separately by specified categorization, i.e. procedure-related vs. device-related. N, percentage and exact Clopper-Pearson 95% CI of the variables will be provided in each category.

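### The treatment-arm procedure- and device-related SAE outcome is labelled CEC-adjudicated, but three of its seven components are sent to the CEC automatically only in part

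*Protocol*

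**What the plan says.** The outcome has seven components, lettered a to g in the protocol synopsis and SAP 3.1.4: perforation (a), dissection (b), embolization to a new territory (c), access-site complication needing repair or transfusion (d), intra-procedural death (e), in vivo breakage (f), and a catch-all (g). Protocol 4.4 gives the same list without letters.

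- **Definition.** SAP 3.1.4 counts these events through 24 (-6/+24) hours "post randomization (time zero) as adjudicated by the clinical events committee, and defined as" the seven components. The synopsis and Protocol 4.4 say the same.
- **Component g.** Protocol 4.4 words it as "any other complications adjudicated by the CEC to be related to the procedure".
- **Table.** SAP 5.4: "The number of Subjects with SAEs will be summarized by CEC adjudicated category described as above", split into procedure-related and device-related, with exact Clopper-Pearson intervals.
- **Routing.** Protocol 13.2.1 makes the CEC responsible for perforation, dissection, symptomatic ICH, embolization to a new territory, all deaths, and "Neurological worsening (associated with a 4 or more point increase in NIHSS) or possible or confirmed evolution/progression of the index stroke". A second list is handled differently: "In cases where their expertise is required the CEC will be asked for an opinion on the following events". For that list the sponsor's "safety department will be responsible for their initial review and coding and they will not automatically be sent to the CEC for adjudication". It contains in vivo device failure, access-site complication needing repair or transfusion, and "Other confirmed or suspected Procedure and/or Device-related SAEs with an outcome other than death occurring at any time during subject participation".
- **Device failures.** Protocol 11.3 has them recorded on their own CRF within 24 hours and says they are not adverse events in themselves.

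**The concern.** A reader of the final table will take each row as the finding of a committee that, under Protocol 13.2.1, has no affiliation with the sponsor. For three of the seven rows the plan does not guarantee this. The device's sponsor codes the event first, and the trigger for asking the CEC, a need for its expertise, has no stated criterion.

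The consequence differs by row. In d and f, an event that the CEC never saw may be counted under a CEC heading. In g, such an event cannot be counted, because CEC adjudication is part of the definition. The sponsor's referral choice can therefore decide whether a residual procedure-related complication appears in the outcome.

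A smaller and separate mismatch concerns the investigator's causality grades. The protocol and the SAP use different scales, and one protocol grade has no counterpart in the SAP.

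**Working it through.** The plan gives no figure to reproduce here. The check is a cross-map of the outcome components against the two lists in Protocol 13.2.1, followed by the arithmetic for one omitted subject.

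**Step 1. Components against routing**

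| Component | Sent to the CEC automatically? | Basis in Protocol 13.2.1 |
|---|---|---|
| a perforation | yes | first list |
| b dissection | yes | first list |
| c new-territory embolization | yes | first list |
| d access-site complication | only if fatal or accompanied by a first-list event | second list |
| e intra-procedural death | yes | all deaths |
| f in vivo breakage | only if fatal or accompanied by a first-list event | second list |
| g other procedure-related | only if fatal or itself a first-list event | second list |

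Four of seven components (a, b, c, e) always reach the CEC. Three (d, f, g) do so only in part.

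**Step 2. What remains of g.** Appendix B includes symptomatic ICH among procedure-related SAEs ("symptomatic ICH, embolization to a new territory, or access site complication requiring surgical repair or blood transfusion"), although a to f do not name it. Whichever row holds it, it is on the first list and reaches the CEC. So does neurological worsening of 4 or more NIHSS points. The exposed part of g is therefore the residual: non-fatal, procedure-related, inside the 24 (-6/+24) hour window and not on the first list. The second-list item is wider than this, since it also covers device-related and merely suspected events at any time. Only the part that overlaps g matters here.

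**Step 3. Direction of error.** For g, an unreferred event fails the definition and is left out, so non-referral can only lower the row. For d and f, the sponsor could code an event in or out differently from the CEC, and the documents give no basis for a direction.

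**Step 4. Source of row f.** SAP 5.4 counts subjects with SAEs. Protocol 11.3 keeps a device failure out of adverse event reporting unless a clinical event results. The breakage is still recorded on a CRF, but SAP 5.4 does not say that this form feeds row f.

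**Step 5. Size of one omission in row g.** Inputs are the minimum of 150 and maximum of 500 subjects and 1:1 allocation (Protocol 8.1). The denominator is taken as all subjects randomized to the treatment arm.

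- Arm size: 150/2 = 75 and 500/2 = 250.
- Change per omitted subject: 1/75 = 1.3 points and 1/250 = 0.4 points.

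The total would be the true residual-g rate multiplied by the share not referred. Neither is given, so no total is computed.

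**Step 6. Causality grades (separate).** Protocol 11.1 has *Unrelated*, *Possible*, *Probable* and *Highly Probable*. SAP 5.1 has *Unrelated*, *Related* and *Unknown*. *Related* carries nearly the protocol's text for *Probable*, and *Highly Probable* fits there by inference. *Unknown* means too little information, which is not what *Possible* means. *Possible* therefore has no SAP category, although SAP 5.2 plans summaries by relationship.

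**The case against.** Tiered referral is a legitimate way to run an adjudication committee. A repair or transfusion, or a device broken in the vessel, largely defines itself, so independent review adds least for d and f. Protocol 13.2.1 still allows the CEC to be asked, and says that committee procedures are in the CEC charter. The charter was not available for this review and may contain referral rules. Safety oversight does not depend on this routing: Protocol 12.3 and 13.2.2 have the DMC review all SAEs in both arms, and SAP 5.2 tabulates all adverse events and SAEs by randomized arm. The outcome is secondary, single-arm and descriptive, with no between-arm test. The 75-subject case is also an edge case, because SAP 4.13.3 allows stopping for expected success only from 200 subjects.

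All of this limits the importance of the point, and most of it stands. It does not remove the conflict. If tiered referral is intended, the definition and the table should say so. A charter rule could close the gap in practice, but Protocol 13.2.1 would still contradict Protocol 4.4 and SAP 3.1.4 and 5.4 as written. DMC review and the general SAE tables protect participants and show the events elsewhere, but they do not make d and f CEC-adjudicated or restore an uncounted g event.

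**Conclusion.** The conflict is real and modest. Followed as written, the plan does not ensure that non-fatal d, non-fatal f and residual non-fatal g events are adjudicated as the outcome definition states. Rows d and f may carry a CEC label that some events have not earned. Row g can only be too low, by 0.4 points per omitted subject at 250 and 1.3 points at 75. This rests on the protocol text alone and assumes that the charter adds no automatic referral.

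A reader might infer more, and the documents do not support it:

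- *Row g mixes CEC and sponsor decisions.* It cannot, because an unreferred event is outside its definition. Mislabelling concerns d and f only.
- *The outcome is understated by some sizeable amount.* With no event rates and no referral shares, any total would be arithmetic on invented inputs. Supposing that nothing is referred would also ignore the referral clause.
- *Serious neurological harm or the primary safety outcome is affected.* Symptomatic ICH, neurological worsening and all deaths go to the CEC automatically.

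The causality mismatch is minor. It affects only the descriptive summaries by relationship in SAP 5.2, not the CEC-adjudicated table.

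**What to change.** 1. **Route the events.** In Protocol 13.2.1, send every treatment-arm candidate SAE for d, f and procedure-related g within the 24 (-6/+24) hour window to the existing CEC. The cost is a small number of extra dossiers. At one event per subject, each percentage point of treatment-arm subjects with such an event adds 0.75 dossiers at 75 and 2.5 at 250.
2. **If d and f are not routed,** label those two rows as sponsor-coded unless referred in Protocol 4.4 and SAP 3.1.4 and 5.4. This is wording only, but it gives up the claim of independent adjudication for them. Relabelling does not repair row g. Residual g candidates must either be referred or, when unreferred and judged related, be shown in a separate sponsor-coded row.
3. **Row f.** State in SAP 5.4 that the row also draws on the device-failure CRF of Protocol 11.3. No new data are needed.
4. **Causality scale (minor).** Reconcile Protocol 11.1 and SAP 5.1 to the scale on the CRF. If four grades are collected, tabulate *Possible* separately and state that it is not counted as *Unrelated* or *Unknown*. This is wording only.

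None of these changes affects randomization, treatment or the primary analysis.

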13.3 Imaging Core Labs

The independent angiographic core lab will review angiographic images from the procedure to determine revascularization and clot location.

The independent CT/MR core lab will review CT/MR images obtained at baseline and at 24 (-6/+24) hours post randomization to determine vessel patency, hemorrhage, and extent of infarcts.

Centralized imaging core labs will be used in this study to provide consistent, independent evaluation of images for confirmation of inclusion criteria. Sites will be provided with instructions for how images should be collected and submitted to Stryker NV within 2 weeks of acquisition of the final required imaging time point at 24 (-6/+24) hours after the procedure. If this timeline cannot be met for any reason, the site should communicate this delay to Stryker NV so that the pending images can be tracked until received.

Ideally MR imaging will be used whenever possible to screen subjects for inclusion into the trial. However, if MR imaging is contraindicated or is unavailable then CT based imaging may be utilized.

STRYKER CONFIDENTIAL - THIS DOCUMENT CONTAINS CONFIDENTIAL AND PROPRIETARY INFORMATION THAT IS THE PROPERTY OF STRYKER CORPORATION. NEITHER THIS DOCUMENT NOR THE INFORMATION HEREIN MAY BE REPRODUCED, USED, OR DISCLOSED TO ANY THIRD PARTY WITHOUT THE PRIOR WRITTEN CONSENT OF STRYKER CORPORATION

Document Number: CDM10000146

Ideally the same imaging modality used at baseline will be used at 24 (-6/+24) hours post randomization. However, for subjects with compromised renal function who had a CT/CTA at baseline, but in whom the treating physician wishes to avoid an additional load of contrast, an MRI/time-of-flight MRA of the intracranial arteries may be obtained instead.

An imaging core lab charter will ensure that consistent policies and procedures are applied throughout the imaging core lab review and determination process. Stryker NV is responsible for tracking images received, requesting required imaging from the sites, performing basic verification of the images received, archiving all images, transmitting and tracking images sent to the core labs, and forwarding the applicable results to the CEC.

13.3.1 Angiographic Core Lab

For each enrolled subject, angiograms must be appropriately de-identified, and sent to the imaging core lab for evaluation. It is important that the images be saved in native DICOM format, and that all imaging sequences are sent (without pre-selecting specific frames). It is also important that the imaging sequences are captured chronologically and are clearly labeled with date and time stamps so that they can be correlated to pre-procedure, post-retriever, and post-procedure time points. Specific imaging transmittal instructions will be provided to the sites by Stryker NV and/or the imaging core lab.

The Angiographic Core Lab will provide an independent assessment of all angiographic inclusion criteria, as well as the secondary efficacy endpoint of modified TICI reperfusion scores post device and post procedure. Additional angiographic scales of interest will also be assessed, including but not limited to AOL, TIMI, and Collateral Flow grade. Refer to **Appendix C** for a description of the scales to be assessed by the Angiographic Core Lab, and the scoring systems that will be used.

13.3.2 CT/MR Core Lab

Baseline and 24 (-6/+24) hour multi-modal CT or MRI imaging will be collected and submitted to the CT/MR Core lab to assess for vessel patency, hemorrhage, and core infarct volume. Vessel patency will be assessed in the Intra cranial ICA; MCA M1 (proximal to striates & distal to striates); MCA M2 (inferior/superior branches); ACA A1; Basilar (proximal, mid, distal segments); and P1 at baseline and at 24 (-6/+24 hours) using CTA/MRA according to the following scale:

0 - occluded

- 1 partial patency
- 2 patent

N/A - not available or able to assess (based on available imaging)

Hemorrhages will be assessed by CT or MRI and will be categorized according to the ECASS III definitions [103] and/or as RIH, IVH, Subdural, Epidural, or SAH. See Table 7.

Document Number: CDM10000146

Rev: AD

Core infact volume will be measured by MR-DWI or CTP-rCBF maps at baseline, and by MRI T2 Flair or CT at later time points.

Table 7. Intracranial Hemorrhage Types

HI-1	Small petechiae within ischemic field without mass effect
HI-2	Confluent petechiae within ischemic field without mass effect
PH-1	Hematoma within ischemic field with some mild space-occupying effect but
	involving $\leq 30\%$ of the infarcted area
PH-2	Hematoma within ischemic field with space-occupying effect involving >
	30% of the infarcted area
RIH	Any intraparenchymal hemorrhage remote from the ischemic field
IVH	Intraventricular hemorrhage
Subdural	Blood between the dura mater and the arachnoid mater
Epidural	Blood between the dura mater and the skull
SAH	Subarachnoid hemorrhage

14 Ethical Considerations

14.1 Compliance with Good Clinical Practices (GCP)

The Investigator will ensure that this study is conducted in accordance with the ethical principles that have their origins in the Declaration of Helsinki and that are consistent with GCP and applicable regulatory (local) requirements; whichever affords the greater protection to the subject.

14.2 Institutional Review Board/ Ethics Committee

A copy of the protocol, proposed Informed Consent form, other written subject information, and any proposed advertising material must be submitted to the IRB/EC for written approval. A copy of the written IRB/EC approval of the protocol and Informed Consent form must be received by Stryker NV before recruitment of subjects into the study and shipment of investigational product.

The Investigator must submit and, where necessary, obtain approval from the IRB/EC for all subsequent protocol amendments and changes to the Informed Consent form. The Investigator must notify the IRB/EC of deviations from the SAEs/UADEs occurring at the site and other SAE/UADE reports received from Stryker NV in accordance with local IRB/EC procedures and regulations.

The Investigator is responsible for obtaining annual IRB/EC approval and renewal throughout the duration of the study. Copies of the Investigator's reports and the IRB/IEC continuance of approval must be sent to Stryker NV.

Document Number: CDM10000146

